3.4. Stratification, Randomization, and Blinding/Masking

This is a single-arm open-label study. There are no plans for stratification, randomization, or masking.

4. Selection of Participants

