8.5.5. Research Assessments

- **Blood for Serum Biomarkers** will be drawn at Visit 1 (Day 0) and Visit 4 (Day 25).
- **Blood for Cellular and Proteomic studies** will be drawn at Visit 1 (Day 0) and Visit 4 (Day 25).
- **UVB Exposure:**
 - A UV Lamp (Ultralite Enterprises Model 36P10A 10-UNV or equivalent device) will be identified by model name and number, and manufacturer at each site. The same device will be used for all phototesting at each site. The UVB dose, based upon the distance from the UV lamp to the participant, will be determined using dedicated photometer and probe prior to each use.

Phototesting will occur at the study site. A photo-barrier template will be placed on non-lesional skin of the participant's exposed lower back/buttock. The template will be placed on the right lower back/buttock for the phototest on Visit 1 (Day 0) and on the left lower back/buttock for the Visit 4 (Day 25) test. UV irradiation will be applied to the template area via a UV Lamp (Ultralite Enterprises Model 36P10A 10-UNV or equivalent device), and every 40 seconds a single template square of the barrier will be covered until all 8 template squares have been covered (i.e., total exposure ranges from 10-80 mJ/cm²).

Before initiating phototesting at Visit 4 (Day 25), the participant should meet all the following criteria:

- The participant must have completed at least 21 days of IP dosing.
 - For individuals whose Visit 4 (Day 25) has been delayed (See Section 8.1.1, *Exception to Visit Windows*), the 21 days starts from the day IP dosing is resumed.
- The participant must confirm that no IP doses have been missed in the prior 7 days. Dosing will be tracked on a paper patient diary and in the EDC (Electronic Data Capture) system.
- The participant must have taken at least 84% of expected daily doses from the day of the first IP dose. Compliance is based on a pill count conducted at Visit 4 (Day 25).

- For individuals whose Visit 4 (Day 25) has been delayed (See Section 8.1.1, *Exception to Visit Window Rules*), compliance should be computed from the day IP dosing is resumed.

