If a participant fails to bring the IP pill bottle(s) back at Visit 4 (Day 25), UVB exposure may proceed during this visit. However, site personnel must confirm at least 84% compliance via a visual pill count prior to the erythema assessment and biopsy at Visit 5 (Day 26). If 84% compliance is not achieved, participant may resume IP dosing. Once the participant has completed appropriate IP dosing, the UVB exposure will be conducted on a site on the lower back, above the original. If the participant does not take the final dose of IP the morning of Visit 5 (Day 26), the erythema assessment and biopsy will still take place, as long as the participant is compliant with their IP dose the 7 days prior to Day 26.

- **Erythema Assessment:**

At Visit 2 (Day 1) and Visit 5 (Day 26), erythema levels for unexposed skin and each template square of the UVB-exposed skin will be quantified using a Chroma Meter (Minolta Model CR-400 or equivalent device). To determine the MED, first compute the average of all the unexposed skin's a* (redness) readings and add 2.5. The lowest exposure with the site's average a* (redness) readings at or above this value is the MED. All skin types (except for Fitzpatrick VI) can be expected to show a response within the planned exposure range[26].

- **Skin Biopsy:** At the indicated time points, 6mm-diameter punch biopsies of nonlesional skin are planned at 3 sites as follows:

1. On Visit 2 (Day 1), 3 biopsy sites on the right buttock include (1) unexposed skin, (2) skin exposed to the 1x MED, and (3) skin exposed to the UVB dose that is 1 step higher than the 1x MED.
2. On Visit 5 (Day 26), 3 biopsy sites on the left buttock will be comparable to those taken on Visit 2 (Day 1), including (1) unexposed skin, (2) skin exposed to the same UVB Dose as the 1x MED from the Visit 2 (Day 1) assessment, and (3) skin exposed to the UVB dose that is 1 step higher than the 1x MED from the Visit 2 (Day 1) assessment. If the 1x MED from the Visit 2 (Day 1) assessment is at the highest UVB dose (80mJ/cm²) or if no erythema is detectable on exposed skin at any dose, then two 4mm biopsies of skin exposed the highest UVB dose will be taken at both Visit 2 (Day 1) and Visit 5 (Day 26).
3. Stitch removal is planned for Visit 3 (Day 14) and Visit 6 (Day 40).

Table 8.2. Schedule of Events

Time Point	Screening	Visit 1	Treatment				Visit 6	Early Termination Visit	Restart Visit ^H	Unscheduled Visit

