13.4.2. Primary Analysis of Primary Endpoint

The primary endpoint is change in percentage of UVB-induced apoptotic epidermal cells from Visit 2 (Day 1) (pre-treatment) to Visit 5 (Day 26) (post-treatment). Percentage of UVB-induced apoptotic cells (A^{UVB}) is defined as the number of TUNEL positive cells in the epidermis divided by the number of nuclei in that high powered field. The percentage of UVB-induced apoptotic cells at a visit is defined as the difference between the percentage of apoptotic epidermal cells in the biopsy exposed at the MED ($A^{Day1MED}$) and percentage of apoptotic epidermal cells in the unexposed biopsy ($A^{unexposed}$), for both biopsies taken at the same visit. The change in percentage of UVB-induced apoptotic epidermal cells will be computed as follows for each individual in the study:

$$A_{Day\ 1}^{UVB} = A_{Day\ 1}^{Day1MED} - A_{Day\ 1}^{Day\ 1\ unexposed}$$

$$A_{Day\ 26}^{UVB} = A_{Day\ 26}^{Day1MED} - A_{Day\ 26}^{Day\ 26\ unexposed}$$

$$\text{change in } A^{UVB} = A_{Day\ 26}^{UVB} - A_{Day\ 1}^{UVB}$$

The null and alternative hypotheses for the primary analysis of the primary endpoint are:

H_0 : Mean change in $A^{UVB} = 0$

H_A : Mean change in $A^{UVB} \neq 0$

The statistical hypotheses outlined above for the mean change in A^{UVB} will be evaluated in the PP1 population using a two-sided Wilcoxon signed-rank test at a Type 1 error rate of 0.05.

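### The pre-treatment phototest is always on the right and the post-treatment test always on the left, so any left-right difference in UVB response is inseparable from the drug effect; counterbalancing is a cheap, low-priority improvement

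*Combined protocol and SAP*

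**What the plan says.** Section 8.5.5 of the combined protocol and SAP assigns the body side by visit, identically for all participants.

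- Phototest before treatment: "The template will be placed on the right lower back/buttock for the phototest on Visit 1 (Day 0").
- Phototest after treatment: "on the left lower back/buttock for the Visit 4 (Day 25) test".
- Biopsies before treatment (Visit 2): "3 biopsy sites on the right buttock include (1) unexposed skin", plus two exposed sites.
- Biopsies after treatment (Visit 5): "3 biopsy sites on the left buttock will be comparable to those taken on Visit 2 (Day 1").
- Repeat exposure when pill-count compliance fails: "the UVB exposure will be conducted on a site on the lower back, above the original". No change of side is stated.

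No section alternates the side, explains the fixed order or adjusts for side in the analysis. Section 3.4 adds: "There are no plans for stratification, randomization, or masking".

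Three provisions bear on how much this matters. Section 13.4.2 defines the visit value as exposed minus unexposed percentage, "for both biopsies taken at the same visit". Section 8.5.5 reads the minimal erythema dose (MED) against the same visit's unexposed redness (a*) plus 2.5. It also requires one UV device per site for all phototests, with the dose determined by photometer and probe before each use.

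**The concern.** The trial has one arm and 10 participants, and its primary result is the within-person change from Visit 2 to Visit 5. Every participant contributes right-before and left-after, so side and treatment period coincide completely. If the left side responds to UVB consistently more or less than the right, or receives a slightly different dose because of positioning, that difference enters each change with the same sign. No later analysis can remove it, because nobody is observed in the opposite order.

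The same order feeds two secondary photosensitivity endpoints, MED and UVB-induced gene expression. The bias could go either way: it could produce a false positive or hide a real effect. Unlike the confounding of time with treatment, which a single-arm before-after design cannot avoid, this one can be removed by design.

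**Working it through.** **What cancels and what does not.** Write b for background apoptosis and u for the UVB-induced part on a given side (R or L), δ for the drug effect and τ for any effect of time.

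- Visit 2: (b_R + u_R) − b_R = u_R
- Visit 5: (b_L + u_L + δ + τ) − b_L = u_L + δ + τ
- Change = δ + τ + s, where s = u_L − u_R

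The backgrounds b drop out. The side difference in UVB response, s, stays in full. If half the participants start on each side, their changes are δ + τ + s and δ + τ − s, so the mean is δ + τ.

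**Inputs.** From sections 13.4.2 and 13.7: 10 pairs, two-sided Wilcoxon signed-rank test at 0.05, SD of the change 15 points, relevant change 20 points. The value of s is not in the documents. I assume 0 to 5 points, in the same direction in every participant, and normal errors.

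**Test size.** With n = 10 the exact test rejects when the smaller rank sum is 8 or less, so its size is 2 × 25/1024 = 4.88%.

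**The plan's own figure.** Section 13.7 states power of at least 93% at 20 points and SD 15% under four distributions. Simulation gives 95.4% (normal), 94.1% (logistic), 92.4% (double exponential) and 95.7% (uniform). The stated figure is reproduced to within a point.

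**Effect of s** (400,000 simulated trials per cell):

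| Assumed s (points) | False positives, fixed sides | False positives, 5/5 split | Power at 20 points, fixed sides, s opposing drug | Power at 20 points, 5/5 split |
|---|---|---|---|---|
| 0 | 4.9% | 4.9% | 95.3% | 95.3% |
| 2 | 6.5% | 4.7% | 90.7% | 95.1% |
| 3 | 8.5% | 4.5% | 87.4% | 94.8% |
| 5 | 15.2% | 3.9% | 78.5% | 93.8% |

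If s favours the drug, fixed-side power is inflated instead, to 97.9%, 98.6% and 99.5% at 2, 3 and 5 points.

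The small power loss under the 5/5 split arises because s becomes spread rather than bias. At 5 points the SD of the changes goes from 15 to about √(15² + 5²) = 15.8.

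**Imbalance among completers.** The residual mean bias is s × (n₁ − n₂)/10, where n₁ and n₂ are the numbers in each order. At s = 5:

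- a 7/3 split leaves 5 × 4/10 = 2 points, and a false-positive rate of about 5.4 to 5.5%;
- an 8/2 split leaves 5 × 6/10 = 3 points, and about 7.5%.

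Both are well below the 15% for fixed sides.

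**The case against.** The strongest reply is that the design already controls most of what could differ between sides. Each visit has its own unexposed biopsy, and the MED is read against that visit's unexposed skin, so differences in background apoptosis or redness cancel. The photometer check and single-device rule deal directly with a dose difference arising from lamp distance. What remains is a side difference in UVB response, or a residual positioning effect, for which the documents offer no evidence. A fixed rule is also simple to follow and keeps the second test off skin already exposed and biopsied, although the protocol does not give that as its reason. All of this stands, and it is why the point has low priority. It does not remove s.

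Three stronger readings are tempting, and the documents do not support them:

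- A reader might infer that any left-right skin difference biases the result, or that the before-after pairing is the trial's only control. The same-visit unexposed biopsy is a second control and removes additive differences.
- A reader might see a contradiction with section 13.3. That section claims only that the measures are free of participant and investigator bias. It makes no claim about anatomical side.
- A reader might expect alternation to be costless and to guarantee a 4.9% ceiling. The ceiling needs near-balanced completers, and non-completers may be replaced at one to three sites, so balance at enrolment can be lost.

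That time remains confounded with treatment is true, but it is no reason to keep a second confounder that can be removed.

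**Conclusion.** The point holds as a minor, avoidable design weakness. Side is completely confounded with treatment for the part of the outcome that the unexposed control does not protect, namely UVB response and residual dose delivery. The size of the bias is unknown. The error rates and power losses shown rest on assumed side differences of 2 to 5 points, a common direction in all participants, SD 15 and normal errors. For scale, the plan's relevant effect is 20 points.

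It would be wrong to infer that the stated alpha or power is incorrect, or that the two sides are known to differ. The stated power reproduces, and the documents are silent on any side difference.

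**What to change.** In section 8.5.5:

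- Counterbalance the first side, half right first and half left first, from one central list covering all sites.
- Use the opposite side at Visits 4 and 5, for both the phototest and the biopsies.
- Give a replacement participant the side order of the participant replaced (section 11.3), so that balance among completers is kept.
- Record the side on the eCRF at each phototest and biopsy.
- Amend section 3.4 to mention the side list.

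The primary test can stay as written. The number of visits, biopsies, UVB exposures and participants does not change.

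The cost is a few sentences, one eCRF field and a check of the recorded side before the Visit 4 exposure. If there is no side difference, no power is lost. If there is one of 5 points, power at the 20-point effect is about 93.8% instead of 95.3%. If enrolment has begun, counterbalancing the remaining participants and recording side still gives partial protection.

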11.1. Participant Completion

Participants must complete Visits 1 (Day 0), 2 (Day 1), 4 (Day 25), and 5 (Day 26) for inclusion in the final analysis of photosensitivity endpoints.

11.2. Participant Withdrawal Criteria

Participants may be prematurely withdrawn from the study for the following reasons:

1. The participant elects to withdraw consent from all future study activities, including follow-up.
2. The participant is “lost to follow-up” under the following conditions:
 - An eligible participant who could not be contacted to schedule Visit 1 (Day 0) within the screening period. Alternatively, this participant may be re-screened.
 - A participant who attended Visit 2 (Day 1) but, at some point during follow-up, attempts to reestablish contact with the participant fail. Attempts to reconnect should continue until Day 25 at which point “lost to follow-up” may be declared.
 - A participant who attended Visit 1 (Day 0), but misses Visit 2 (Day 1) is allowed to re-screen if contact can be reestablished. Otherwise, “lost to follow-up” may be declared.
3. The participant dies.
4. The investigator no longer believes participation is in the best interest of the participant.

If a participant withdraws from the study, the participant will be asked to return for a final visit where the assessments outlined in the early termination visit in Table 8.2, *Schedule of Events*, will be performed. No additional follow-up will be requested from participants after early study withdrawal.

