8.1. Visit Windows

With one exception, described below, study visits should take place within the time limits specified in Table 8.1, *Visit Windows*. The designated visit windows for each scheduled visit are also indicated in Table 8.2, *Schedule of Events*. Whenever possible, a rescheduled visit should remain within the designated visit window. The coordinating center should be notified if the study procedures for any scheduled visit cannot be performed within the designated window.

Table 8.1. Visit Windows

VISIT	Target Day (window)
Screening Period	(Days -30 to -1)
Visit 1	Day 0
Visit 2	Day 1, 24 hours after Visit 1 UVB exposure (within 20-28 hours of Visit 1 UVB exposure)
Visit 3	Day 14 (Days 10 to 15)
Visit 4	Day 25 (Days 21 to 29)
Visit 5	Day 26, 24 hours after Visit 4 UVB exposure (within 20-28 hours of Visit 4 UVB exposure)
Visit 6	Day 40 (Days 36 to 41)

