12.4. Collection and Recording of Adverse Events

12.4.1. Collection Period

Adverse events will be collected and recorded in EDC from Visit 1 (Day 0), until a participant completes study participation or until 30 days after he/she prematurely withdraws or is withdrawn from the study (without withdrawing consent). Serious Adverse Events, as defined in Section 12.2.4 *Serious Adverse Events*, Suspected Adverse Reactions, as defined in Section 12.2.2, *Suspected Adverse Reactions*, and adverse events related to study procedures will be collected and recorded in EDC from the time of consent until a participant completes study participation or until 30 days after he/she prematurely withdraws or is withdrawn from the study (without withdrawing consent).

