12.4.2. Collecting Adverse Events

Adverse events (including SAEs) may be discovered through any of these methods:

- Observing the participant.
- Interviewing the participant [e.g., using a checklist, structured questioning, diary, etc.].
- Receiving an unsolicited complaint from the participant.

In addition, an abnormal value or result from a clinical or laboratory evaluation can also indicate an adverse event, as defined in Section 12.3, *Grading and Attribution of Adverse Events*.

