12.4.3. Recording Adverse Events

Throughout the study, the investigator will record all adverse events and SAEs as described previously (Section 12.2, *Definitions*) on the appropriate AE/SAE eCRF regardless of the relationship to study therapy regimen or study procedure.

Once recorded, an AE/SAE will be followed until it resolves with or without sequelae, or until the end of study participation, or until 30 days after the participant prematurely withdraws or is withdrawn from the study, whichever occurs first (without withdrawing consent).

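### Sections 12.4.1 and 12.4.3 run adverse event collection to 30 days after early withdrawal, but section 11.2 leaves that period without any planned contact

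*Combined protocol and SAP*

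**What the plan says.** Section 12.4.1 sets the collection period for adverse events: from Visit 1 (Day 0) "until a participant completes study participation or until 30 days after he/she prematurely withdraws or is withdrawn from the study". Those who withdraw consent are excepted. Section 12.4.3 follows an event already recorded until it resolves, until study participation ends, or "until 30 days after the participant prematurely withdraws or is withdrawn from the study, whichever occurs first", with the same exception.

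Section 11.2 describes what happens at withdrawal: "the participant will be asked to return for a final visit where the assessments outlined in the early termination visit" in Table 8.2 will be done. It then closes with "No additional follow-up will be requested from participants after early study withdrawal". Section 11.4 mentions only that one visit. Section 8.4 asks for it only when withdrawal comes before Visit 4, whereas 11.2 and 11.4 set no such limit. Table 8.2 lists nothing for a withdrawn participant after the Early Termination Visit.

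Two other provisions matter. Section 6.5.1 keeps Visit 6 for participants who stop tofacitinib permanently; it is in person if the safety event behind the stop was related to study participation, and virtual or by telephone if the stop was not due to a related event. Section 12.4.2 lists the ways in which events come to light, among them "Receiving an unsolicited complaint from the participant".

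**The concern.** The safety sections define a 30-day period, and the withdrawal section plans nothing with which to fill it. A site that keeps to 11.2 makes no call and no visit after the final one. It can record only what the participant volunteers, and it has no planned way to learn how an open event ended.

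Secondary objective 3 concerns safety and toxicity. Section 13.4.1 puts everyone who received any tofacitinib in the Safety Sample, early withdrawals included. Section 13.4.4.3 summarises treatment-emergent events without stating where the observation window ends or how long each person was observed. A withdrawn participant with no contact after the final visit would then look the same in the tables as one who was followed for 30 days without an event. In a study of 10 completers single events carry weight: under section 12.8.2.2, Grade 3 or higher infections in two participants are enough to trigger an ad hoc DSMB review.

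**Working it through.** The plan gives no figure for this point to reproduce. The check sets the passages side by side and then does day arithmetic.

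**1. Who falls into the gap.** Each way of leaving, set against the 30-day rule:

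| Way of leaving | Does the 30-day rule apply? | Planned contact after the final visit |
|---|---|---|
| 11.2 item 1, consent withdrawn for all activities | No, excepted in 12.4.1 and 12.4.3 | None, consistent |
| 11.2 item 2, lost to follow-up | Formally yes | None possible |
| 11.2 item 3, death | Not applicable | Not applicable |
| 11.2 item 4, withdrawn by the investigator | Yes | None, **conflict** |
| Stops drug but stays in the study (6.5.1) | Not a study withdrawal | Visit 6 is kept |

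Item 4 is the listed reason for which the rule applies and can work in practice. An event open at that participant's final visit falls under 12.4.3, again with no contact planned.

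**2. Length of the unsupported period.** For withdrawal on day *w*, collection ends on day *w* + 30. Withdrawal on Day 20, for example, gives 20 + 30 = Day 50. Planned contacts between the final visit and that day: 0.

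**3. Ambiguity inside 12.4.3.** Follow-up ends at the earliest of its listed limits, and one of these is the end of study participation. If withdrawal itself ends participation, the 30-day limit never takes effect. The text does not say which is meant.

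**4. Completers' observation after the last dose.** Inputs:

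- First dose on Day 2, last dose on the morning of Visit 5 (3.1).
- Visit 4 on Day 25, window Days 21 to 29; Visit 5 one day later; Visit 6 on Day 40, window Days 36 to 41 (Table 8.1).
- At least 21 days of dosing completed before the Visit 4 phototest (8.5.5).

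Formula: days observed = Visit 6 day − Visit 5 day.

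- On target: 40 − 26 = 14 days.
- Shortest: latest Visit 5 = 29 + 1 = Day 30; earliest Visit 6 = Day 36; 36 − 30 = 6 days.
- Longest: the 21st dose falls on Day 2 + 20 = Day 22, so the earliest Visit 5 is Day 23; 41 − 23 = 18 days.
- With the Table 8.1 windows alone and no 21-day rule, the earliest Visit 5 is Day 22, giving 41 − 22 = 19 days.

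The range of 6 to 18 leaves out the delay allowed in 8.1.1. There Visit 4 may slip to 12 weeks (Day 84) while Table 8.1 leaves Visit 6 at Days 36 to 41, so the subtraction has no useful meaning.

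**The case against.** The best defence is that 11.2 governs what the site asks of participants, while 12.4.1 governs what goes into the database. A site can request nothing and still enter any event reported within 30 days, and 12.4.2 allows for that. This stands in part: a reader might infer that 11.2 forbids follow-up or recording, and it does not. But passive reporting is no planned means of following an open event to the 30-day limit in 12.4.3.

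Second, most safety-driven stops are dealt with elsewhere, because 6.5.1 keeps Visit 6 for participants who stop drug. That stands, and it confines the gap to withdrawals from the study.

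Third, the size is easily inflated. A reader might add the replacement caps in 11.3 (3 + 18 = 21) and conclude that 21 participants could be affected. Those caps cover anyone who misses the Visit 4 and 5 assessments, including participants who withdraw consent, are lost, stop only the drug or leave before the first dose. They limit replacements and do not estimate this group.

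Fourth, a reader might conclude that completers' safety follow-up is too short, since contraception runs for one month and the live-vaccine restriction for 6 weeks after drug. Those are pregnancy and vaccine precautions. The protocol states no minimum adverse event window after the last dose, so 14 days breaches nothing in it. Nor should 14 be set against 30 as if they measured the same thing: one counts from the last dose, the other from withdrawal.

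Finally, the study has a single arm, so unequal observation cannot bias a comparison between groups. Section 13.4.5 also reports disposition. Both points are correct, but disposition alone does not show how long each person was observed.

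**Conclusion.** The conflict holds as a matter of wording with a practical effect. The protocol states a 30-day period of adverse event collection and follow-up after early withdrawal and plans no contact within it once the final visit is over. It mainly concerns participants withdrawn by the investigator and events unresolved at the Early Termination Visit.

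The number of people involved is unknown, since it depends on how many dosed participants leave by that route, and it may be small. A reader might go further and say that the whole safety objective rests on this gap. The documents do not support that: completers share one nominal window, and drug-only stops keep Visit 6. Primary analysis, sample size and power are untouched.

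The completer range of 6 to 18 days assumes that the last dose is taken on the morning of Visit 5, that the 21-day rule in 8.5.5 is met, and that the 8.1.1 delay is not used. It is something to report, not a defect in itself. Reconciling the sections is worth doing because it is cheap and the information lost is safety information.

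**What to change.** 1. In 11.2, limit the closing sentence to participants who withdraw consent, and bring 11.4 into line.
2. For other withdrawn participants, name one remote contact at the end of the 30 days, using the virtual or telephone format that 6.5.1 already provides, and add it to Table 8.2.
3. Align 8.4 with 11.2 and 11.4 on who is asked to attend the Early Termination Visit, and say in 12.4.3 whether withdrawal counts as the end of participation for the earliest-of rule.
4. In the safety tables, give each participant's days of observation after the last dose, and show withdrawn participants who were not contacted as not observed after their last contact.

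The cost is a wording amendment, one short call for each affected participant and a little more tabulation. No visit, sample or change to the completers' schedule is needed.
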